4.0 Eligibility Criteria

4.1 Patients

4.1.1 Inclusion Criteria

- Age ≥ 18 years
- Cirrhosis based on:
 - biopsy
 - characteristic clinical, laboratory, and imaging findings
- Decompensated cirrhosis as denoted by any of the following:
 - active ascites requiring paracentesis during hospitalization
 - active overt hepatic encephalopathy requiring lactulose during hospitalization
 - active hepatic hydrothorax requiring thoracentesis during hospitalization
- Poor quality of life as defined by:
SF-36 Physical and/or Mental Component Summary scale <40 (1SD below the mean of healthy subjects)^{1, 40}
- Discharged to home, skilled nursing facility, sub-acute rehabilitation care, or long-term acute care
- Able to be consented, either in person or through legally authorized representative
- Access to a telephone

4.1.2 Exclusion Criteria

- Solid organ transplant of any organ
- History of dementing illnesses and other neurodegenerative diseases such as Alzheimer's disease, Parkinson's disease, or vascular dementia
- Unable to complete study questionnaire due to hearing loss
- Legally blind
- Pregnant or nursing
- Incarcerated

- Concurrent enrollment in a related interventional research study

4.2 Caregivers

4.2.1 Inclusion Criteria

- Age ≥ 18 years
- Identified caregiver of patient
- Able to be consented, either in person or through legally authorized representative
- Access to a telephone

4.2.2 Exclusion Criteria

[figure not shown]
- Impaired cognitive function
- Unable to complete study questionnaire due to hearing loss
- Legally blind
- Incarcerated

5.0 Study Design

This is a pilot, randomized controlled trial to establish the feasibility of enrollment, data collection, and outcome assessment for a future efficacy trial. Participants will be enrolled and randomized to the Cirrhosis Medical Home or usual care at the time of hospital discharge and will be followed for 6 months.

The goal of this proposal is to establish the feasibility of a randomized controlled trial comparing the Cirrhosis Medical Home to usual care in improving QOL and health care utilization of patients with decompensated cirrhosis and poor QOL. To achieve this goal, we propose a feasibility study in which we will randomize 40 patients to the Cirrhosis Medical Home or usual care, assessing QOL; physical, cognitive, and psychological symptoms; and health care utilization. Figure 1 shows the conceptual model.³⁸ We hypothesize that the Cirrhosis Medical Home will improve QOL through its effects on physical, psychological, and cognitive recovery, and that this improvement in QOL will result in decreased health care utilization.

Figure 1. Cirrhosis Medical Home Conceptual Model

[figure not shown]
In addition, 40 caregivers of people with cirrhosis will be enrolled in the study. They will complete the Zarit Burden Interview-12 (ZBI-12) at baseline, 3 months and 6 months. For those caregivers who care for participants who are randomized into the CMH arm, the caregivers will complete the HABC-M Caregiver assessment during their interactions with the CMH care coordinator. The HABC-M for the Caregiver is not a study outcome but is an assessment that the care coordinator uses to help guide the individualized care plan for the patient.

6.0 Enrollment/Randomization

Research staff will review the hepatology inpatient census each day, and eligible patients will be approached during their hospital stay. On or close to the day of hospital discharge and after obtaining informed consent, research staff will complete the Baseline Assessment and obtain baseline measurements in all enrolled subjects in both intervention and control arms. Subjects will then be randomized via a computer-generated randomization scheme into the Cirrhosis Medical Home or usual care by separate personnel who will not be involved in outcomes assessments. Research staff who are completing study assessments will be blinded to the assignment. Research staff will be trained research study personnel in the Division of Gastroenterology who will be specifically trained in the study measures. Our research assistants will be trained not to inquire about study assignments. They will be conducting structured assessments that do not provide room for qualitative interviewing that should prevent unblinding. They will not be involved in study assignments and treatment administrations. Subjects will be instructed not to discuss their therapy with the research assistants.

7.0 Study Procedures

Figure 2. Study Flow

ARM 1: Cirrhosis Medical Home

Initial Evaluation: Prior to discharge, the care coordinator will review the hospital discharge plan, obtain the approval of the patient's physicians to co-manage the patient's care, and schedule a face-to-face, telephone, or virtual visit with the patient at their place of discharge. This step is important for relationship-building.

The First Visit: The care coordinator will conduct a face-to-face, telephone, or virtual visit at the patient's location (e.g. home, skilled nursing facility) within 72 hours of hospital discharge. The coordinator will assess the patient's physical, cognitive, and psychological status, and will complete a needs assessment for both the patient and family caregiver. All measures performed by the care coordinator will be used to guide the use of care protocols and development of the individualized care plan. These measures are different from the outcomes measures. The coordinator will also reconcile all medications. The Anticholinergic Cognitive Burden Scale will be completed by study staff. The coordinator will make note of scheduled and recommended appointments and will document initial and follow-up visits in the care coordination support software.

Individualized Care Plan: The care plan will be developed with an emphasis on coordinating services with the patient's providers. Using the assessments from the first visit, the coordinator will collaborate with the Cirrhosis Medical Home interdisciplinary team and the primary care providers to finalize the individualized care plan. This plan will be created through consultation and discussion between the care coordinator and interdisciplinary team using the assessments as guides. The assessments do not automatically trigger protocols or handouts, and there are no firm cutoffs on any of the assessments that would require any specific action. Rather, the assessments will be used to facilitate development of the care plan within the context of the patient's unique individual circumstances. The assessments will also be used to assess for response to any intervention provided, so that appropriate changes to the care plan can be made in a timely fashion. If a patient does not have a participating caregiver, then no caregiver protocols or handouts will be used. Finally, the care coordinator will schedule a second face-to-face, telephone, or virtual visit within two weeks of the first visit.

The Second Visit: During the second visit, the coordinator will review the individualized care plan with both the patient and the family caregiver. This process will include a) reviewing diagnoses; b) reviewing monitoring processes; c) implementation of care protocols; d) explanation of the corresponding educational handouts (patient and family caregiver); and e) connection to in-home services and community resources.

The 6-month Interaction Period: Follow-up includes a 6-month interaction period between the care coordinator, the patients, and the family caregivers via face-to-face visits, phone contact, email, fax, or mail. The minimum amount of contact will be every

two weeks. During these interactions, the coordinator will answer questions; collect patient and caregiver feedback; reconcile medications and discuss adherence; review appointments and care plans; have the patient and the caregiver complete the HABC Monitor to trigger the use of care protocols; and facilitate access to community resources. Additional measures, described in the schedule of events, may be repeated depending on the individualized care plan, active issues, and needs as determined by the study team. The plan will be amended through consultation and discussion between the care coordinator and interdisciplinary team using the assessments as guides. The assessments do not automatically trigger protocols or handouts and there are no firm cutoffs on any of the assessments that would require any specific action. Rather, the assessments will be used to facilitate development of the care plan within the context of the patient's unique individual circumstances. The assessments will also be used to assess for response to any intervention provided, so that appropriate changes to the care plan can be made in a timely fashion. Throughout the follow-up phase, the coordinator will work with patients, caregivers, the Cirrhosis Medical Home team, and the patient's physicians to monitor, implement, and revise the individualized care plan. Such revisions could include introducing discussions about hospice care for patients who develop indications for hospice referral during follow-up. The Cirrhosis Medical Home team and coordinator will meet weekly to discuss new patients and monitor progress. If a patient requires hospitalization, the team activates the acute care transition phase where the coordinator contacts the hospital team and provides relevant information about the patient's symptoms, as well as the patient's most updated medication list. Following any hospital discharge, the coordinator will conduct a home, telephone, or virtual visit within 72 hours to reconcile medications and coordinate the post-discharge care plan. At the end of 6 months, all patients will be transitioned to receive full care by their primary care and specialty physicians.

ARM 2: Usual Care

Prior to hospital discharge, the care coordinator will identify the primary care and/or hepatology provider of patients in the usual care group and will ensure follow up appointments at the time of hospital discharge. The coordinator will compose and send a letter to the primary care and/or hepatology provider summarizing the patient's diagnosis, hospital course, discharge medications, and the plan of follow-up care. If the patient does not already have a primary care or hepatology provider, the coordinator will work with the patient to identify a new provider. Subjects in this group will receive no further intervention.

Outcome Assessment (Both Arms)

Outcome measures will be obtained by blinded research staff from all enrolled subjects at baseline, 3 months, and 6 months. Baseline assessments will be completed in the hospital at the time of enrollment. Outcomes at 3 and 6 months will be completed in person. If participants are not able to attend in person, measures that can be performed remotely will be done via phone or videoconference.

8.0 Study Personnel

8.1 Research Staff

8.1.1. Recruitment Staff/Assessors: Trained research staff from the Division of Gastroenterology will be trained to administer the study measures in Section 3. They will recruit patients, obtain informed consent, complete the Baseline Assessment and measurements at the time of enrollment. They will be blinded to the study assignment as detailed in Section 6. They will also complete outcomes assessments at 3 and 6 months.

8.1.2. Randomization Staff: A separate member of the research team will be responsible for randomization so that the outcomes assessors will be blinded to the assignment.

8.2 Care Coordinator

The coordinator is a registered nurse whose scope of practice includes health coaching, case management, community organization, and nursing care. The coordinator will conduct home visits; collaborate with the interdisciplinary team; communicate with the patient's physicians; conduct root-cause analysis for unplanned acute care; implement individualized care plans; and monitor the care plans' effectiveness. The coordinator will be supervised by the interdisciplinary team. This person will conduct face to face, telephone, or virtual visit with those in the intervention arm in the hospital, within 72 hours of discharge, and again within 2 weeks (the first and second visits). They will meet with the CMH interdisciplinary team weekly throughout the study to review patients. They will assess patients using the several instruments detailed in the schedule of events, which will be used to help develop individualized care plans and which will be used to guide specific care protocols. They will interact with study participants at least every 2 weeks during the 6-month follow-up period. For those randomized to usual care, they will help ensure follow-up after discharged as detailed in Section 7, but will not have any further contact with study participants. The care coordinator will not perform any of the outcomes assessments. The coordinator will be trained in all study procedures and instruments.

8.3 CMH Interdisciplinary Team

The Cirrhosis Medical Home support team will consist of two hepatologists (Drs. [name] and [name]), a geriatrician with expertise in collaborative care ([name]), a health services researcher ([name]), and a pharmacist ([name]). The team will meet weekly with the care coordinator. [name] will be accessible to the coordinator through phone or pager at all times. The team will supervise the care coordinator and ensure appropriate care.

9.0 Data Safety Monitoring

This is a minimal risk study and not a drug treatment trial. As such, adverse events are expected to be minimal in both number and nature. However, all such events or other subject problems/complications will be reported in accordance with federal, state, local, and university guidelines.

10.0 Study Withdrawal/Discontinuation

Participants who choose to withdraw from the study will do so by contacting the study coordinator or [name] directly at [contact]. This information will be given to participants as part of the informed consent process and ongoing communication between participants and study staff.

11.0 Statistical Considerations

This is a pilot trial for feasibility and effect size estimation. The plan is to enroll 40 total patients and randomize in 1:1 ratio to the Cirrhosis Medical Home and usual care. As a pilot trial, the study is not powered to test efficacy, but is designed to generate preliminary data to support a larger future trial. The sample size of 40, enrolled over 9 months (see study timeline in section 13), will allow for recruitment of approximately one patient/caregiver dyad per week. Data collected from this pilot will be used to provide an estimate of intervention effect, i.e. the difference in the primary outcome measure (SF-36) between intervention and control groups. The pilot data will also provide estimates on variability in the outcome measures in this patient population. The effect and variability estimates from the pilot data will be used to power a large trial. The sample size of 40 will provide 80% probability that the 95% confidence interval for the estimated treatment difference with half-width of 0.7SD will contain the true treatment effect. The pilot sample size of 40 has also been shown to minimize the overall sample size of the pilot and the main trial together with 80% power in the main trial to detect effect sizes in the range of 0.1~0.3SD.⁶⁷

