2.0 Objective(s)

- 2.1** The primary objective of this trial is to test the screening and enrollment processes for a randomized controlled trial of the Cirrhosis Medical Home compared to usual care for patients with decompensated cirrhosis and poor quality of life when discharged from the hospital
- 2.2** Secondary objectives are:

- 2.2.1 to assess the data collection process, outcome assessment, and the acceptability of the Cirrhosis Medical Home trial
- 2.2.2 to estimate the effect size of the Cirrhosis Medical Home intervention on quality of life at six months post hospital discharge

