3.2 Secondary Outcome Measures

3.2.1. Quality of Life: This outcome will be obtained from the patient only. Patient health-related QOL will be assessed using the Medical Outcome Study Short Form (SF-36).^{40, 48, 49} This scale has eight components (physical functioning, role-physical, bodily pain, general health, vitality, social functioning, role-emotional, and mental health) that are aggregated into a Physical Component Summary (PCS) and a Mental Component Summary (MCS). Changes that differ by 2 or more points on a scale of 0 to 100 are clinically meaningful.⁴⁹

3.2.2 Physical Performance: Physical performance measures will be obtained from the patient only. Physical recovery will be assessed via the Short Physical Performance Battery (SPPB), a validated objective assessment.⁵⁰ The SPPB yields a performance score of 0-12 (0-4 poor, 5-7 intermediate, 8-12 good). A difference of 1 point indicates significant change in function. The SPPB has been validated in patients with decompensated cirrhosis.^{51, 52} Grip strength will also be obtained to calculate the Liver Frailty Index, <https://liverfrailtyindex.ucsf.edu>, which overlaps with the SPPB.

3.2.3 Depression and Anxiety Symptoms: Depression and anxiety symptoms will be obtained from the patient only. The Patient Health Questionnaire-9 (PHQ-9)^{53, 54} and Generalized Anxiety Disorder Scale (GAD-7)^{55, 56} will be used to measure patient mood and anxiety. The PHQ-9 is a nine-item depression scale with a total score from 0 to 27, and the GAD-7 is a seven-item anxiety scale with a total score from 0 to 21. Both of these scales are derived from the Patient Health Questionnaire, have good internal consistency and test-retest reliability as well as convergent, construct, criterion, procedural and factorial validity for the diagnosis of major depression and general anxiety disorder.

3.2.4 Cognitive Assessment: Cognitive assessment will be obtained from the patient only. 3D CAM and PHES are psychometric measures of hepatic encephalopathy. They are quick, simple paper tests that are easily interpreted. They are components of the gold-standard Psychometric Hepatic Encephalopathy Score.⁵⁷⁻⁶⁰

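### The SF-36 effect estimate has no stated baseline adjustment, although baseline SF-36 is collected before randomization and adjusting for it would usually narrow the interval

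*Combined protocol and SAP*

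**What the plan says.** Objective 2.2.2 is "to estimate the effect size of the Cirrhosis Medical Home intervention on quality of life at six months post hospital discharge". Section 11.0 is the only place that says how: the effect is "the difference in the primary outcome measure (SF-36) between intervention and control groups". That sentence names no model, covariate or change score. It does not choose between the Physical and Mental Component Summaries (PCS and MCS, Section 3.2.1), and it gives no time point. No other section fills these gaps.

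Section 11.0 justifies 40 patients, randomized 1:1, by attaching 80% probability to a "95% confidence interval for the estimated treatment difference with half-width of 0.7SD". It states the purpose of the estimates: "The effect and variability estimates from the pilot data will be used to power a large trial". It also cites a pilot-sizing argument based on "80% power in the main trial to detect effect sizes in the range of 0.1~0.3SD".

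The baseline score will be available. Under Section 6.0, research staff "complete the Baseline Assessment and obtain baseline measurements in all enrolled subjects in both intervention and control arms", and randomization follows. Section 7.0 (Outcome Assessment) says "Outcome measures will be obtained by blinded research staff from all enrolled subjects at baseline, 3 months, and 6 months". A PCS and/or MCS below 40 is also an entry criterion (Section 4.1.1). Section 6.0 mentions a computer-generated scheme but no stratification or balancing on SF-36.

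**The concern.** Effect and variability estimation is one of the two statistical purposes that Section 11.0 gives the pilot, and precision is part of its case for 40 patients. With 20 per arm and no balancing on SF-36, the arms will often differ at baseline by chance. An unadjusted 6-month comparison carries part of that gap into the estimate, whereas ANCOVA removes the part that baseline predicts.

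Two things are at stake. The first is the width of the interval for the effect. The second is which variability is passed to the main trial: a trial analysed by ANCOVA is sized on the residual SD, or on the raw SD and the correlation, and the plan does not say which will be reported. Leaving the model open also allows unadjusted, change-score and adjusted estimates to be compared after the data are seen.

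**Working it through.** **Inputs from the documents:** 20 patients per arm, 95% CI, half-width 0.7SD, probability 80%, main-trial effects of 0.1 to 0.3SD (all Section 11.0). **Assumed:** the correlation *r* between baseline and 6-month SF-36, which the documents do not give, and no dropout unless stated. Widths are in units of the raw outcome SD.

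**1. The plan's own figure.** A 95% interval covers the true value 95% of the time by construction, so the 80% is read here as the chance that the half-width is at most 0.7SD.

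- Unadjusted half-width = t(0.975, 38) × √(2/20) = 2.024 × 0.316 = 0.640SD.
- P(half-width ≤ 0.7SD) = P(χ²₃₈ ≤ 38 × (0.7/0.640)²) = 0.810.

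This agrees with the stated 80%. Other readings do not: a fixed ±0.7SD interval has 97.3% coverage, and power to detect 0.7SD is 60.0%.

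**2. ANCOVA on baseline.** Half-width = t(0.975, 37) × √[0.1 × (1 − r²) × (1 + 1/36)], where the last factor allows for chance baseline imbalance. The probabilities in the table come from 200,000 simulated trials per value of *r* (bivariate normal, 20 per arm).

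| Assumed r | Half-width (SD) | P(half-width ≤ 0.7SD) |
|---|---|---|
| Unadjusted | 0.640 | 81% |
| 0 | 0.650 | 77% |
| 0.2 | 0.636 | 82% |
| 0.3 | 0.620 | 88% |
| 0.5 | 0.563 | 98% |
| 0.7 | 0.464 | >99% |

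The two methods are equal at r = 0.17. ANCOVA is 1.5% wider at r = 0 (0.650/0.640), 3% narrower at r = 0.3 (0.620/0.640) and 12% narrower at r = 0.5 (0.563/0.640).

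**3. Effect of the entry rule.** Suppose the below-40 criterion cut the baseline SD by 30% (assumed, k = 0.7). Then r′ = rk/√(1 − r² + r²k²). Correlations of 0.3, 0.5 and 0.7 become 0.22, 0.38 and 0.57. The half-widths become 0.63, 0.60 and 0.54SD, with probabilities of 83%, 92% and 99%.

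**4. Chance imbalance.** The baseline mean difference has SD √(2/20) = 0.316SD, so P(|gap| > 0.3SD) = 2 × [1 − Φ(0.3/0.316)] = 0.34. A 0.3SD gap moves the unadjusted estimate by r × 0.3SD: 0.09, 0.15 and 0.21SD at r = 0.3, 0.5 and 0.7. This explains the wider unadjusted interval in step 2; it is not a further error on top of it.

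**5. How well the pilot would estimate r.** Fisher's z with n = 40 gives tanh(atanh(r) ± 1.96/√37). Observed values of 0.3, 0.5 and 0.7 have 95% CIs of −0.01 to 0.56, 0.22 to 0.70 and 0.50 to 0.83.

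**6. Consequence for the main trial.** At 80% power and two-sided 5%, an assumed r = 0.5 lowers the total from 350 to 262 at 0.3SD, and from 786 to 590 at 0.2SD.

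**The case against.** The plan is silent on adjustment; it does not rule it out, and an ANCOVA coefficient is also a difference between groups. The match in step 1 needs the sentence to be re-read. If SD there meant a residual SD, an ANCOVA interval would give about 77% to 81%, so the match does not prove that an unadjusted analysis was intended. **This stands.** The case for the change rests on what the plan leaves unstated, not on a mistake in it.

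The gain depends on an unknown *r*. Baseline is measured in hospital during decompensation, follow-up is six months later, and entry is restricted on the score, so *r* could be low and the gain negligible. **This also stands.** Against it, the loss is at most about 1.5% in expected width.

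The primary aims are feasibility, and even 0.56SD does not make effects of 0.1 to 0.3SD estimable. That is true, but effect-size estimation is still a stated objective, and the variability estimates are meant to be used.

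Attrition may matter more. An assumed 20% loss (16 per arm) widens the unadjusted half-width to 0.722SD and cuts the 81% to 44%. That is a separate problem and not a reason to leave the model unspecified. Fewer analysed patients also raise the break-even correlation slightly, to about 0.20 at 15 per arm.

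A mixed model using the 3-month scores is a reasonable alternative, provided that it also adjusts for baseline and is fixed in advance.

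**Conclusion.** The concern holds, as an improvement in efficiency and pre-specification rather than a correction of an error. The plan gives the SF-36 effect only as a between-arm difference, and its precision statement agrees with an unadjusted comparison under the reading in step 1. A valid baseline covariate is already collected in every patient.

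The size of the benefit is uncertain. It ranges from 1.5% wider at r = 0 to 12% narrower at r = 0.5, and more at higher correlations, assuming 20 analysed per arm. The case for reporting the raw SD, residual SD and correlation does not depend on *r* being large. Each needs its interval, because 40 patients estimate *r* imprecisely.

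**What to change.** Replace the Section 11.0 sentence on the intervention effect with text such as:

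> The intervention effect at 6 months (objective 2.2.2) will be estimated separately for SF-36 PCS and SF-36 MCS by ANCOVA, with treatment and the baseline value of the same score as covariates, and reported with a 95% CI. The raw SD, the residual SD and the baseline-to-6-month correlation will be reported, each with a 95% CI, for main-trial planning.

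Section 11.0 also calls SF-36 the primary outcome measure, while Section 3.2 lists it as secondary. If the planned main trial is meant, say so.

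The cost is two sentences and one degree of freedom per model, with no new data. This wording does not settle how deaths and missing 6-month scores are handled, which needs its own decision.

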3.0 Study Measures

All primary and secondary outcomes measures will be obtained from study participants at baseline and at 3 and 6 months, per the schedule of events. Additionally, MELD and Child-Pugh scores will also be obtained at the 3 and 6 month assessments.

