3.1 Primary Outcome (Feasibility) Measures

3.1.1. Enrollment rate: The enrollment rate is the number of patients/caregivers enrolled per month. We will further determine the number of patients/caregivers screened and approached for enrollment. Based on these numbers, we will calculate the proportion of screened patients/caregivers eligible for enrollment, the proportion of eligible patients/caregivers approached, and the proportion of approached patients/caregivers enrolled. Of those not eligible, we will record reasons for ineligibility. Of those eligible, but not approached, we will record reasons. For those approached, but not enrolled, we will record reasons.

3.1.2 Drop-out rate: The drop-out rate is the proportion of enrolled participants (patients and caregivers) who drop out of the study before completion.

3.1.3 Data completion: We will record the completeness of the data collection for enrolled subjects. For those with incomplete data, we will record reasons that data could not be collected.

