The results of this study will establish the feasibility of performing a randomized trial to evaluate the efficacy of the Cirrhosis Medical Home in improving QOL for patients with decompensated cirrhosis. The next step will be to conduct a large-scale efficacy trial.

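### Section 11 will power the main trial on the pilot's effect estimate and fixes no target difference; used as the target, that estimate sizes the trial within a factor of 2 in only about 9/18/26% of pilots (true effect 0.1/0.2/0.3 SD)

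*Combined protocol and SAP*

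**What the plan says.** Section 11.0 plans 40 patients randomized 1:1. It defines the intervention effect as the between-arm difference in SF-36 and then says: "The effect and variability estimates from the pilot data will be used to power a large trial". The effect estimate and the variability estimate are thus given the same role.

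The section describes the pilot's precision as a "95% confidence interval for the estimated treatment difference with half-width of 0.7SD", with an 80% probability attached. It also defends the size of 40 by reference to a main trial with "80% power in the main trial to detect effect sizes in the range of 0.1~0.3SD". That is a range of effects to be detected; no single target is chosen from it.

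Section 3.2.1 offers a possible target: "Changes that differ by 2 or more points on a scale of 0 to 100 are clinically meaningful". Section 11.0 does not refer to it. Section 3.2.1 also describes two SF-36 summary scores, PCS and MCS, and neither is named as the score for sizing. Objective 2.2.2 is to estimate the effect on quality of life at six months. The closing paragraph of Section 3 makes the later trial the purpose of the exercise: "The next step will be to conduct a large-scale efficacy trial".

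**The concern.** Required sample size varies with one over the square of the target difference, so error in the target is magnified. A pilot of 40 measures the SD fairly well and the effect badly. If the observed difference is used as the target, the size of the main trial is settled mostly by chance. A chance-large difference gives a trial too small for the true effect. A zero or wrong-direction difference gives no usable number. A chance-small difference gives a trial far larger than needed.

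With a target fixed in advance, power is set for a difference judged worth detecting. Lower power for smaller true effects is then a deliberate choice. At stake is the reliability of the efficacy trial that this pilot exists to support.

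**Working it through.** **Inputs.** From Section 11.0: 20 patients per arm, 80% power, and effects of 0.1, 0.2 and 0.3 SD, used here only as test values. Assumed: two-sided alpha 0.05 (not stated for the main trial), normal outcome, everyone analysed and no baseline adjustment unless noted.

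**The plan's own figure.** The SE of the difference is SD × √(2/20) = 0.316 SD. With t(38) = 2.024 the half-width is 2.024 × 0.316 = 0.640 SD when the sample SD equals the true SD. The probability that it is at most 0.7 SD is P(χ²₃₈ ≤ 38 × (0.7/0.640)²) = 0.81. The stated 80% therefore reproduces as an assurance on interval width. Against the effects of interest, 0.7/0.3 = 2.3 and 0.7/0.1 = 7.

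**Required size.** n per arm = 2 × ((1.960 + 0.8416)/d)², which gives 1570, 393 and 175 for d = 0.1, 0.2 and 0.3.

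**Plug-in use, closed form.** Planned n is within a factor of 2 of required n when the pilot estimate lies between d/√2 and d√2. At d = 0.2 the window is 0.141 to 0.283, so the probability is Φ(0.262) − Φ(−0.185) = 0.603 − 0.426 = 0.177. The same step gives 0.089 at d = 0.1 and 0.262 at d = 0.3.

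**Plug-in use, simulated.** These are 1,000,000 pilots per scenario with the SD also estimated. Planned n per arm is 2 × (2.8016/d̂)² when d̂ > 0, and true power is Φ(d√(n/2) − 1.960).

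| True effect (SD) | 0.1 | 0.2 | 0.3 |
|---|---|---|---|
| n within a factor of 2, all pilots | 9% | 18% | 26% |
| n within a factor of 2, right-direction pilots | 14% | 24% | 31% |
| Zero or wrong direction, no n | 38% | 26% | 17% |
| n below half the requirement | 45% | 40% | 35% |
| n above double the requirement | 9% | 16% | 22% |
| Mean true power, right-direction pilots | 37% | 53% | 62% |

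**Sensitivity of the all-pilots, within-factor-2 row.** The plan gives no baseline correlation or attrition rate, so these values are assumed.

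- Baseline adjustment, correlation 0.5: 10/20/29%.
- Baseline adjustment, correlation 0.7: 12/24/35%.
- 30% loss (14 per arm): 7/15/22%.
- Correlation 0.7 with 30% loss: 10/20/29%.
- True effect 0.5 SD, above the cited range: 41%.

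**Comparator: target fixed at 0.2 SD** (2 points if the SD is 10), with only the SD taken from the pilot. Planned n per arm is 2 × (2.8016 × s/0.2)², where s is the pilot SD. When the true effect equals the target:

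| True effect 0.2 SD | Fixed target | Plug-in |
|---|---|---|
| n within a factor of 2, all pilots | 99.5% | 18% |
| n per arm, 10th to 90th percentile | 282 to 511 | 34 to 3,424* |
| Power at 10th/50th/90th percentile | 66/79/89% | 13/44/100%* |
| Pilots reaching 80% power, all pilots | 47% | 23% |

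*Right-direction pilots only.

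When the true effect is not 0.2 SD, the fixed-target n is not meant to match it. It falls within a factor of 2 of the requirement for the true effect in 0.02% of pilots at 0.1 SD (mean power 29%) and in 33% at 0.3 SD (mean power 98%).

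**A 2-point target in patients.** 2 × (2.8016 × SD/2)², rounded up, is 252, 393 or 566 per arm at assumed SDs of 8, 10 or 12.

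**The case against.** **Plug-in use is not stated.** The estimate could inform a go/no-go decision, or a check that a chosen target is plausible. This stands, and every plug-in figure above is conditional on it. Still, the sentence gives the effect the same role as the SD and adds no safeguard, so plug-in is the natural reading.

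**The section does bound the effects of interest.** If the estimate were held within 0.1 to 0.3 SD, the within-factor-2 figures would be about 55/18/61% and mean power 52/74/89%. That would be a clear improvement at the ends of the range and none in the middle. The plan states no such bound.

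**The measure flatters a fixed target.** The 99.5% requires the true effect to equal the target. At a true 0.1 SD, a 0.2 SD target does worse than plug-in on this measure (0.02% against 9%) and on mean power (29% against 37% among right-direction pilots). This is correct. The case for fixing the target is that power is then set for a difference worth detecting, and low power below it is chosen in advance. It does not make the trial the right size for every possible truth.

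**Scope.** The pilot's primary objective is screening and enrollment, it is expressly not powered for efficacy, and the later trial will have its own protocol. This is also true, and it limits the weight of the point. But Section 11.0 already states a rule for that later trial, and a rule is most credible when set before the pilot result is known.

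**Conclusion.** The concern holds. Section 11.0 commits the pilot's effect estimate to powering the large trial, and no section fixes a target difference. Under plug-in use, main-trial size is within a factor of 2 of the requirement in about 9/18/26% of pilots at true effects of 0.1/0.2/0.3 SD. Across the attrition and baseline-adjustment values tried, the figure stays between 7% and 35%.

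The result rests on plug-in use, a normal outcome and a true effect in the range Section 11.0 cites. The choice of alpha and power does not affect it, because both cancel in the ratio of planned to required n. This is a worthwhile and cheap improvement, not an error in the conduct of the pilot.

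**What to change.** Replace the sentence quoted from Section 11.0 with:

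> The pilot SD of a named SF-36 summary score (PCS or MCS), or its residual SD after baseline adjustment, and patient attrition will be used to size the large trial. The target difference will be a prespecified clinically meaningful difference on that score, for example the 2 points in Section 3.2.1. The pilot effect estimate and its 95% CI will be reported descriptively and will not be used as the target difference.

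Attrition should be taken for patients alone, since the drop-out rate in Section 3.1.2 counts patients and caregivers. Optionally, size on an upper confidence limit of the pilot SD: with the point estimate, only 47% of pilots reach 80% power even when the true effect equals the target.

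The cost is one sentence replaced by three, with no added patients, visits or data, and objective 2.2.2 is kept. The downsides are that the team must choose PCS or MCS, that the resulting n may look large beside one based on a chance-large pilot effect, and that a fixed target accepts low power for smaller true effects.
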